2.3 Potential Risks and Benefits

2.3.1 Potential Risks

The potential risks of participating in this trial are those associated with having blood drawn, the IM injection and possible reactions to the HEV-239 vaccine with aluminum adjuvant, and breach of confidentiality.

Drawing blood may cause transient discomfort and fainting. Fainting is usually transient and managed by having the subject lie down and elevate his/her legs. Bruising at the blood draw site may occur but can be prevented or lessened by applying pressure to the blood draw site for a few minutes after the blood is taken. IM injection may also cause transient discomfort and fainting. Drawing blood and IM injection may cause infection. The use of aseptic (sterile) technique will make infection at the site where blood will be drawn or where the study vaccination will be given extremely unlikely.

There is a small amount of risk to subjects who report that they are in good health but who may have an unknown health problem at the time of screening. This trial will screen by physical exam, history, and vital signs. The following baseline laboratories will be obtained at screening on all subjects to determined eligibility.

Baseline Laboratories:

- Hematology
 - Complete blood count with differential (which will include white blood cells, the absolute neutrophil count (ANC), the absolute eosinophil count (AEC), hemoglobin, and platelets).
 - A WBC evaluation may include any abnormal cells, which will then be reported by the laboratory. A hematology evaluation may include abnormalities in the red blood cell (RBC) count and/or RBC parameters

DMID/NIAID/NIH

CONFIDENTIAL

and/or RBC morphology, which will then be reported by the laboratory. In addition, any other abnormal cells in a blood smear will also be reported.

- Chemistry (fasting or non-fasting)
 - o Creatinine
 - o Glucose
 - Alanine aminotransferase (ALT)
- Serology
 - Hepatitis B surface antigen
 - Hepatitis C antibody
 - HIV types 1 and 2 antigen/antibody
 - Hepatitis E virus IgM and IgG antibodies
- Serum pregnancy test (in women of childbearing potential)
- Urine
 - A urine drug screen will be obtained

Safety laboratories will be obtained on Day 8 after each vaccine dose and also before the Day 180 vaccination. To minimize risks, subjects will not receive the subsequent study vaccinations if a related Grade 3 laboratory abnormality occurs. The following safety laboratories will be obtained on all subjects to determined safety.

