5.2 Requirements Prior to Administration of the Second and Third Vaccinations

The following assessments should be performed prior to the administration of the second and third vaccinations to determine if the subject remains eligible:

Subjects will not receive the subsequent vaccine doses (first or second boost) if any of the prespecified individual halting criteria are met (see below and Section 8.6.2).

- For a woman of childbearing potential, an acceptable form of birth control must be verified. A urine pregnancy test must be performed and the subject must not be pregnant before administering the vaccine.
- Subjects who do not meet inclusion criteria 2 4 and 7 11, and exclusion criteria 7 21 will not be given the second or third vaccination.
- Subjects who have a fever (defined as an oral temperature ≥38.0°C) or a moderate or severe acute illness at the time of or in the three days prior to boost vaccination administration may have the boost vaccination deferred until they recover as long as this remains within the study window (see Section 6.3).
- Subjects who do not receive the second dose of vaccine for any reason will not receive the third dose of vaccine.

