5.3 Withdrawal from the Study, Discontinuation of Study Product, or Study Termination

5.3.1 Withdrawal from the Study or Discontinuation of the Study Product

Subjects may voluntarily withdraw their consent for study participation at any time without penalty or loss of benefits to which they are otherwise entitled.

DMID/NIAID/NIH

An investigator may also withdraw a subject from receiving the study product for any reason. Follow-up safety evaluations and blood draws will be conducted, if the subject agrees. If a subject withdraws or is withdrawn prior to completion of the study, the reason for this decision must be recorded in the electronic case report forms (eCRFs).

The reasons, might include, but are not limited to the following:

- Subject no longer meets eligibility criteria
- Subject meets individual halting criteria (reference to Section 8.6.2)
- Subject becomes noncompliant
- Medical disease or condition, or new clinical finding(s) for which continued participation, in the opinion of the investigator might compromise the safety of the subject, interfere with the subject's successful completion of this study, or interfere with the evaluation of responses
- Subject lost to follow-up
- Subject becomes pregnant, if applicable
- Determined by a physician's discretion to require additional therapy not indicated in the protocol to ensure subject's health and well-being (or treatment failure, if applicable)

The investigator should be explicit regarding study follow-up (e.g. safety follow-up) that might be carried out despite the fact the subject will not receive further study product. If the subject consents, every attempt will be made to follow all AEs through resolution. The procedures that collect safety data for the purposes of research must be inclusive in the original informed consent or the investigator may seek subsequent informed consent using an IRB/IEC-approved consent form with the revised procedures.

The investigator will inform the subject that already collected data will be retained and analyzed even if the subject withdraws from this study.

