6.3.1.3 Visit 04, Day 15 +/- 2 Days; Clinic Visit

- Obtain vital signs (HR, BP, and oral temperature)
- Perform symptom-directed PE (if needed)
- Evaluate vaccination site (if needed)
- Interview the subject and review the e-Memory aid data. Address any incomplete, missing, or inconsistent data.
- Review of Unsolicited AEs and SAEs.
- Counsel subjects to use adequate birth control methods to avoid pregnancy
- Review concomitant medications.
- Obtain blood for safety laboratories (if needed due to abnormalities at prior visit, Section 2.3.1)
- Obtain serum for immunogenicity assays
- Collect PBMCs and plasma for future assays.

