8.1.1.1 Adverse Events Grading

All AEs (laboratory and clinical symptoms) will be graded for severity and assessed for relationship to study product (see definitions). AEs characterized as intermittent require documentation of onset and duration of each episode. The start and stop date of each reported AE will be recorded on the appropriate data collection form and eCRF. Changes in the severity of an AE will be documented to allow an assessment of the duration of the event at each level of intensity.

Severity of Event:

AEs will be assessed by the investigator using a protocol-defined grading system (toxicity table included as an appendix). For events not included in the protocol-defined grading system, the following guidelines will be used to quantify severity:

- Mild (Grade 1): Events that are usually transient and may require only minimal or no treatment or therapeutic intervention and generally do not interfere with the subject's usual activities of daily living.
- Moderate (Grade 2): Events that are usually alleviated with additional specific therapeutic intervention. The event interferes with usual activities of daily living, causing discomfort but poses no significant or permanent risk of harm to the research participant.

DMID/NIAID/NIH

• Severe (Grade 3): Events interrupt usual activities of daily living, or significantly affects clinical status, or may require intensive therapeutic intervention. Severe events are usually incapacitating.

Relationship to Study Product: The assessment of the AE's relationship to study product will be done by the licensed study physician indicated on the Form FDA 1572 and the assessment will be part of the documentation process. Whether the AE is related or not, is not a factor in determining what is or is not reported in this trial. If there is any doubt as to whether a clinical observation is an AE, the event should be reported.

In a clinical trial, the study product must always be suspect. The relationship to study product will be assessed for AEs using the terms related or not related:

- Related There is a reasonable possibility that the study product caused the AE. Reasonable possibility means that there is evidence to suggest a causal relationship between the study product and the AE.
- Not Related There is not a reasonable possibility that the administration of the study product caused the event.

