8.4 Type and Duration of Follow-up of Subjects after Adverse Events

Solicited AEs are reactogenicity events occurring on the day of each study vaccination through Day 8 after each study vaccination. Unsolicited AEs are non-serious adverse events occurring from the time of the first study vaccination until Day 57, then from Day 180 through Day 208. AEs will be assessed, and followed from initial recognition of the AE through end of the protocol defined follow-up period. AEs will be followed to adequate resolution. Resolution of an AE/SAE is defined as the return to pretreatment status or stabilization of the condition with the expectation that it will remain chronic.

DMID/NIAID/NIH

SAEs will be collected from the time of the first study vaccination through the last study visit (Day 360). SAEs will be followed to adequate resolution or stabilization even if this extends beyond the study-reporting period.

Follow-up procedures, evaluations, and outcomes will be recorded on the appropriate eCRF.

8.5 Procedures to be Followed in the Event of Abnormal Laboratory Test Values or Abnormal Clinical Findings

Samples will be collected for hematology, serum chemistry and urinalysis. The study clinician licensed to make medical diagnoses and listed on the Form FDA 1572 as the site principal investigator or sub-investigator must review the laboratory results, document this review, and record attribution to study product and clinical significance for all abnormal laboratory values on the Local Laboratory eCRF. Abnormal laboratory results meeting the protocol-defined toxicity grading scale are considered adverse events; however, they ARE NOT reported as unsolicited AEs on the Adverse Event eCRF. The laboratory reports must be filed with the source documents.

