8.6.2 Individual Halting Criteria

Individual subjects will not be administered boost vaccination doses (2nd or 3rd vaccination) if he or she experiences ANY of the following:

- Anaphylaxis within 1 day after administration of a study vaccine.
- Allergic reaction (e.g., generalized urticaria) within 3 days after administration of a study vaccine.
- A serious adverse event (SAE) that is considered to be study vaccine-related.
- A severe (grade 3) laboratory adverse event that is considered to be study vaccine-related and persists for 3 or more days.
- A severe (grade 3) unsolicited adverse event that is considered to be study vaccine-related and does not resolve or decrease to a lower grade.

DMID/NIAID/NIH

DMID Protocol 15-0108	Version 2.0
Phase I Study of HEV-239	08 FEB 2019

- A severe (grade 3) solicited systemic adverse event that is considered to be study vaccinerelated and persists for 3 or more days and does not resolve or decrease to a lower grade (Subjective systemic reaction corroborated by study personnel).
- A severe (grade 3) solicited injection site adverse event that persists for 3 or more days and does not resolve or decrease to a lower grade. (The size [measured in mm] of ecchymosis, erythema, and induration/swelling will not be used as a halting criterion).

Vaccinations for an individual subject may be suspended for safety concerns other than those described above, at the discretion of the investigator if he/she feels the subject's safety may be threatened. The investigator may ask for an *ad hoc* SMC meeting to be held for any single event or combination of multiple events which, in his/her professional opinion, could jeopardize the safety of the subjects or the reliability of the data.

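### Protocol 2.3.1 stops later doses after any related Grade 3 laboratory abnormality; Protocol 8.6.2 and SAP 6.6 also require it to last at least 3 days, and nothing says which text prevails

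*Protocol*

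**What the plan says.** Protocol 2.3.1 (Potential Risks) sets out the safety laboratory schedule and then states that "subjects will not receive the subsequent study vaccinations if a related Grade 3 laboratory abnormality occurs". The event must be related and Grade 3. No duration is mentioned.

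Protocol 8.6.2 (Individual Halting Criteria) lists events after which a subject will not be given dose 2 or dose 3. Its laboratory entry reads "A severe (grade 3) laboratory adverse event that is considered to be study vaccine-related and persists for 3 or more days". SAP 6.6 repeats this entry in the same words.

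The texts that connect the two rules are these:

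- Protocol 8.5 states that "Abnormal laboratory results meeting the protocol-defined toxicity grading scale are considered adverse events".
- Protocol 5.2, the section on requirements before doses 2 and 3, states that "Subjects will not receive the subsequent vaccine doses (first or second boost) if any of the prespecified individual halting criteria are met" and refers to 8.6.2. Protocol 5.3.1 also cites 8.6.2 among the reasons for stopping study product.
- Protocol 8.6.2 adds that "Vaccinations for an individual subject may be suspended for safety concerns other than those described above, at the discretion of the investigator".
- Protocol 8.1.1.1 requires changes in severity to be "documented to allow an assessment of the duration of the event at each level of intensity".
- Protocol 7.2.1.2 requires abnormal laboratory events to be followed until they resolve or become clinically stable.
- The planned recheck, at Visit 04 (6.3.1.3) and Visit 08 (6.3.1.7), is conditional: "Obtain blood for safety laboratories (if needed due to abnormalities at prior visit, Section 2.3.1".

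**The concern.** Both sentences are mandatory and both are in the current protocol, yet they give different answers for the same subject. After a short-lived related Grade 3 value, a site working from 8.6.2 may give a dose that 2.3.1 says will not be given. A site working from 2.3.1 withholds a dose that the laboratory criterion in 8.6.2 does not bar.

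The rule is an individual safety stop before doses 2 and 3. Under 5.2 a subject who misses dose 2 for any reason also loses dose 3, so the choice of text can decide the rest of that subject's vaccination series.

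**Working it through.** The plan gives no figure on this point to reproduce. The check compares the texts and then examines the visit windows.

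**Step 1: is it the same event?** Section 2.3.1 speaks of a laboratory abnormality and 8.6.2 of a laboratory adverse event. Under 8.5 an abnormal result that reaches the toxicity scale is an adverse event, so a Grade 3 abnormality is a Grade 3 laboratory adverse event. Both texts also require relatedness. The only difference left is duration.

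**Step 2: where do the rules differ?**

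| Related Grade 3 value | Protocol 2.3.1 | Laboratory criterion in Protocol 8.6.2 and SAP 6.6 |
|---|---|---|
| Lasts 3 days or more | Withhold | Withhold |
| Lasts under 3 days | Withhold | Not triggered |
| Duration not established | Withhold | Text does not settle it |

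**Step 3: can the third row occur under the planned visits?** Inputs: Visit 03 is Day 8 +/- 1, so Day 7 to 9. Visit 04 is Day 15 +/- 2, so Day 13 to 17. Dose 1 is Day 1.

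- First draw to recheck: shortest 13 - 9 = 4 days; longest 17 - 7 = 10 days.
- Dose to first draw: 7 - 1 = 6 to 9 - 1 = 8 days, with no safety draw planned in between, so onset is not observed.
- Dose to recheck: 13 - 1 = 12 to 17 - 1 = 16 days.

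Visits 07 and 08 (Days 36 and 43) have the same windows counted from dose 2, so the same gaps apply.

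Suppose a value arises after the dose, is Grade 3 at the first draw and is lower at the recheck. It may have been Grade 3 for less than 3 days, or for almost the whole 12 to 16 days between dose and recheck. The planned draws alone cannot place it on one side of the 3-day line.

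If the recheck is still Grade 3 and the episode is read as continuous, at least 4 days have passed. Both rules then withhold and there is no conflict.

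**Step 4: does any text settle the order?** Sections 5.2 and 5.3.1 cite 8.6.2. Neither mentions the sentence in 2.3.1 or says that 8.6.2 overrides it. SAP 6.6 repeats 8.6.2 without comment.

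**The case against.** The strongest reply is that the working rule can be identified. Section 2.3.1 is a risk narrative. The section that governs doses 2 and 3 is 5.2, and it sends the site to 8.6.2 alone. Section 5.3.1 does the same, and SAP 6.6 repeats the criterion. On this view one background sentence is out of line and sites are unlikely to diverge. Much of this stands: 8.6.2 is the more likely list in practice. But a cross-reference is not a statement of precedence, and the visit sections send site staff to 2.3.1 for the safety laboratories. The study-level laboratory rule in 8.6.1 has no persistence condition either, so the wording in 2.3.1 cannot be dismissed as an obvious slip. That study-level rule needs two or more subjects and does not settle the individual rule.

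Three stronger readings are tempting, and the documents do not support them.

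- A reader might infer that 8.6.2 is the only bar to dosing, so that a short Grade 3 value obliges the site to vaccinate. It does not. Section 8.6.2 allows discretionary suspension, 5.3.1 lets the investigator withdraw a subject from study product for any reason, and 5.2 re-applies investigator-judged eligibility criteria. These routes permit withholding, whereas 2.3.1 requires it, so they soften the conflict without removing it.
- A reader might infer that no follow-up of a Grade 3 value is required. Section 7.2.1.2 requires it. Only the timing of the draws is left open.
- A reader might extend the point to the sample drawn before dose 3 at Day 180. Nothing requires that result to be known before the dose is given. That is a different question from the contradiction between the two rules, and this point does not rest on it.

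**Conclusion.** This is an internal inconsistency in a mandatory individual safety stop. It is narrow but should be fixed. It affects only related Grade 3 laboratory values that last under 3 days or whose duration the draws do not establish. For values known to last 3 days or more, the texts agree.

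The documents give no rate for such values and none is assumed, so the number of subjects affected among the 25 planned cannot be estimated. The statistical effect is negligible: the protocol describes the study as exploratory with no formal hypothesis test, and its sample-size table does not depend on this rule. A reader might infer a threat to the safety or immunogenicity estimates; nothing in the documents supports that.

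The conclusion rests on reading 8.5 as making the two terms equivalent, and on the absence of any ranking in the protocol and SAP as provided. The 4 to 10 day gap assumes visits within their windows and no unscheduled draw. Unscheduled visits under 6.4 may supply one, but its timing is not set.

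**What to change.** Reconcile Protocol 2.3.1, Protocol 8.6.2 and SAP 6.6 so that all three carry one identical Grade 3 laboratory rule, chosen by the sponsor's medical team. If that rule keeps a persistence condition, state how persistence is judged from the draws actually taken, including when a recheck is no longer Grade 3. No clinical rule is proposed here.

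The cost of the reconciliation is wording: a protocol clarification or amendment, with ethics board approval before implementation where it is an amendment (Protocol 9.1), and a matching SAP edit if the chosen rule differs from the present 8.6.2 text. Reconciliation itself adds no subjects, visits or procedures. A persistence definition that relied on additional draws would add some, and that choice also belongs to the sponsor.

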3 STUDY DESIGN, OBJECTIVES AND ENDPOINTS OR OUTCOME MEASURES

3.1 Study Design Description

This is a Phase I double-blind, randomized, placebo controlled trial (1:4 ratio of placebo to vaccine) of HEV-239 in 25 US males and non-pregnant females ages 18 - 45 (inclusive) to assess the safety, reactogenicity, and immunogenicity of HEV-239. Subjects will receive 3 doses of study product on Days 1, 29, and 180 (Table 1: Study Groups). Subjects will remain in the study for up to 13 months (including screening). Subjects and study staff will be blinded to a subject's study vaccine assignment. This vaccine is a 239 amino acid sub-fragment of the 660 amino acid HEV structural protein that is produced in *E. coli*.

Table 1: Study Groups

Study Group	Number of Subjects	First Dose (Day 1, Visit 01)	Second Dose (Day 29, Visit 05)	Third Dose (Day 180, Visit 11)
HEV-239 Vaccine	20	HEV-239	HEV-239	HEV-239
Placebo	5	Placebo	Placebo	Placebo
Total	25			

• The HEV-239 vaccine dose contains 30 micrograms of purified protein adsorbed to 0.8 mg aluminum hydroxide suspended in 0.5 mL buffered saline, and thimerosal.

• The placebo will be 0.9% Sodium Chloride Injection, USP (Normal Saline) is a sterile, nonpyrogenic, isotonic solution of sodium chloride and Water for Injection (WFI). A total of 0.5 mL will be administered which contains sodium chloride 4.5 mg. It contains no bacteriostatic, antimicrobial agent, preservatives, or added buffer and may contain hydrochloric acid and/or sodium hydroxide for pH adjustment (pH 5.3 [4.5 to 7.0]).

Thorough medical history, physical examination (PE), and screening laboratory tests (see **Sections 7.1** and **7.2**) will be obtained at screening after informed consent is obtained. Each subject may be screened beginning 28 days prior to the prime vaccination. At Day 1, the inclusion and exclusion criteria will be reviewed prior to randomization. Subjects who sign an informed consent and meet all inclusion criteria and no exclusion criteria will be enrolled in the study.

DMID/NIAID/NIH

Subjects will be observed for 30 minutes after vaccination. The occurrence of solicited injection site and systemic reactogenicity events will be measured from the time of study vaccination through Day 8 after each vaccination. These will be ascertained through use of an electronic Memory (e-Memory) aid, a telephone call on Day 4 after each dose of vaccine, a Day 8 clinic visit, and potentially at the Day 15 clinic visit after each dose of vaccine. Unsolicited AEs will be collected from vaccination through D29 after each vaccination. SAEs will be collected from the time of the first study vaccination through the last study visit (Day 360).

The study includes multiple phlebotomy time points for immunogenicity and blood collection for future use at Visit 1 and Days 8, 15, and 29 after each vaccination. The durability of the immune response and future use collection will be assessed at 5 months after the first boost (Day 180) and at 6 months after the second boost (Day 360).

Note: The study day and the day after boost vaccination may not always align due to the study windows (See Appendix A) for the appropriate windows of time for each study visit.

Schematic of Study Design: See Figure 1.

3.2 Study Objectives

3.2.1 Primary

- Assess the safety and reactogenicity of HEV-239 following delivery of each vaccine dose.
- Assess the number of subjects with \geq 4 fold rise in HEV IgG at any time after vaccination.

